**CONFIDENTIAL**

### 3.3.2 $\alpha$ -cell Function (contingent on funding)

- A. Hyperglycemic clamp-derived measures:
  - a. Glucagon suppression in response to sustained hyperglycemia during the clamp (the decrement in glucagon concentration from baseline to nadir value at 100-120 minutes)
  - b. Acute glucagon response to arginine (the incremental increase in glucagon concentration from pre-arginine baseline for the 10 minutes after the arginine injection)
- B. OGTT-derived measures: integrated glucagon response from 0-120 minutes
- C. Fasting measures: glucagon

### 3.3.3 Insulin Sensitivity

- (i) Hyperglycemic clamp-derived measures: glucose disposal rate at steady state (100-120 minutes) divided by ambient insulin concentrations
- (ii) OGTT-derived measures:
  - a. Matsuda index
  - b. Model-derived insulin sensitivity
- (iii) Fasting measures:
  - a. 1/fasting insulin,
  - b. HOMA-S (using the Oxford calculator),
  - c. QUICKI

### 3.3.4 Blood and Urine Biomarkers

- (i) Glycemic control: HbA1c (baseline predictor, and as a time-dependent treatment outcome)
- (ii) Adipokines/inflammatory markers: adiponectin; others contingent on funding (see list above in Section 2.8.1)
- (iii) Non-esterified fatty acids
- (iv) Renal/vascular: urinary albumin/creatinine ratio at baseline (contingent on funding)

### 3.3.5 Physical Measures

- (i) Physical measures: blood pressure, body weight, body mass index, waist and hip circumference

## **3.4 Treatments**

### **3.4.1 Three-week Placebo Run-in Phase**

Prior to randomization, eligible volunteers will participate in a 3-week run-in period. They will be instructed by study staff in proper injection technique and will receive three weeks of both placebo injections and tablets. At the end of the placebo-run in period, they will return any unused medication which will be counted to assess adherence. Participants taking <80% of the medication will be excluded from further participation.

Those who have been compliant with medication use ( $\geq 80\%$ ) will be eligible to participate and will undergo the baseline study procedures. Once these are completed, and if willing to undergo these tests repeatedly as required by the study, they will be randomized to one of the treatment arms and will enter the active treatment phase. In addition, after completing the first set of study procedures, they will receive instruction in lifestyle modification, including individualized instruction on weight loss, exercise and diet.

### **3.4.2 Twelve-month Active Treatment Phase**

Participants will be randomized to one of the four interventions. Participants will be seen every three months throughout the study and will be given three months of medication at a time during the active treatment phase. Study staff will monitor compliance by auditing returned medication every three months. Participants randomized to insulin will be required to perform home blood glucose monitoring.

Participants randomized to metformin monotherapy will not know whether they have been assigned to metformin or placebo. Double blinding of these two groups will be done to minimize dropout of those participants assigned to placebo.

The two groups receiving injectables (i.e., liraglutide and insulin glargine) will not be masked to the intervention.

All medications used in RISE are approved for treating type 2 diabetes and will be used according to the label; Investigational New Drug (IND) applications will be obtained for use of all medications in individuals with prediabetes. For study procedures performed during the active phase of treatment, study medications will be withheld on the morning of testing.

### **3.4.3 Metformin**

Initiation and determination of maintenance dosing for metformin will be the same in all treatment groups, although the timing of undertaking these steps differs by treatment group.

**CONFIDENTIAL**

To minimize non-compliance due to gastrointestinal side effects, participants will be titrated over four weeks from a starting dose of 500 mg once daily to a maximum dose of 1000 mg bid. Participants will remain on the maximum tolerated dose of metformin throughout the study. If participants are unable to tolerate metformin they will continue in the study but will not take the medication.

#### **3.4.4 Liraglutide plus Metformin**

Liraglutide will be started at a dose of 0.6 mg subcutaneously, once daily. This dose will be continued for one week, after which subjects will increase the daily dose to 1.2 mg if they have tolerated the 0.6 mg daily dose. Likewise, after one week at 1.2 mg daily, the dose will be increased to 1.8 mg daily, the maximal recommended daily dose in the treatment of diabetes. If participants cannot tolerate the higher dose, they will revert back to the previously tolerated dose and will remain on that maximal tolerated daily dose for the duration of the study. Once the maximal dose of liraglutide has been reached and is tolerated, metformin will be initiated and titrated as described above. If the combination of the medications produces intolerable adverse effects, liraglutide treatment will be retained in preference to metformin.

#### **3.4.5 Insulin Glargine Followed by Metformin**

Insulin will be titrated over a period of one month based on self blood glucose monitoring to achieve a fasting blood glucose of 80-90 mg/dl without hypoglycemia, and then continued with dose adjustment to maintain the fasting glucose in this range. Insulin glargine has been shown to be titratable in individuals with prediabetes and established diabetes to achieve fasting glucose concentrations of <95 mg/dl without a marked increase in recurrent or severe hypoglycemia [44]. Following 3-months of insulin treatment, insulin glargine will be discontinued and metformin will be commenced and titrated as above.

#### **3.4.6 Placebo**

Matching metformin placebo will be titrated equivalently to the active metformin. Adverse effects and final dosing achieved will be recorded in parallel with active metformin.

#### **3.4.7 Medication Wash-out and Post-treatment Follow Up**

Following the completion of the intensive re-assessments (hyperglycemic clamp and OGTT) after 12 months of the intervention, study medications will be stopped and the participants will continue to be followed off medications, for a minimum of 3 months and up to 9 months, depending on the time of randomization within the 5-year study period. At the end of the first 3 months off treatment (i.e., 15 months after randomization), the hyperglycemic clamp and OGTT will be repeated to determine the durability of the effects of the active interventions on  $\beta$ - and

$\alpha$ -cell function. Although it is unlikely in this study population, participants may experience deterioration in  $\beta$ -cell function during this 3-month wash out period, and require rescue therapy. Criteria for rescue, and protocol-specified rescue therapy, are described below (see Section 7.4). Participants who do not require rescue will undergo the final clamp and OGTT procedures at the end of the 3-month washout period. They will then continue to remain off study medications and retesting will occur 9-months following discontinuation of the intervention (i.e., 21 months after randomization). The rescue protocol will be utilized, as needed, during this last 6-month follow-up period. Following the complete 9-month washout period, patients will be referred to their primary care provider for further follow up.

### **3.4.8 Rescue**

The approach to rescuing a participant with severe hyperglycemia is described in Section 7.4.

## **3.5 *Inclusion Criteria***

1. Fasting plasma glucose 95-125 mg/dl *plus* 2-hour glucose  $\geq$ 140 mg/dl on 75 gm OGTT *plus* HbA1c  $\leq$ 7.0%. There is no upper limit for the 2-hour glucose on OGTT.
2. Age 20-65 years
3. Body mass index (BMI)  $\geq$ 25 kg/m^2 ( $\geq$ 23 kg/m^2 in Asian Americans) but  $\leq$ 50 kg/m^2
4. Self-reported diabetes <1 year in duration
5. Drug naïve (no prior to oral glucose lowering agent(s), insulin or other injectable glucose lowering agents)

## **3.6 *Exclusion criteria***

1. Underlying disease likely to limit life span and/or increase risk of intervention or an underlying condition that is likely to limit ability to participate in outcomes assessment
2. An underlying disease that affects glucose metabolism other than type 2 diabetes
3. Taking medications that affect glucose metabolism, or has an underlying condition that is likely to require such medications
4. Active infections
5. Renal disease (eGFR <45 mL/minute/1.73 m)
6. Anemia (hemoglobin <11 g/dl in women, <12 g/dl in men) or known coagulopathy

7. Cardiovascular disease, including uncontrolled hypertension. Participants must be able to safely tolerate administration of intravenous fluids required during clamp studies.
8. History of conditions that may be precipitated or exacerbated by a study drug:
  - a. Pancreatitis
  - b. Serum ALT more than 3 times the upper limit of normal
  - c. Excessive alcohol intake
  - d. Suboptimally treated thyroid disease
  - e. Medullary carcinoma of the thyroid or MEN-2 (in participant or a family history)
  - f. Hypertriglyceridemia (>400 mg/dl despite treatment)
9. Conditions or behaviors likely to affect the conduct of the RISE Study
  - a. Unable or unwilling to give informed consent
  - b. Unable to adequately communicate with clinic staff
  - c. Another household member is a participant or staff member in RISE
  - d. Current, recent or anticipated participation in another intervention research project that would interfere with any of the interventions/outcomes in RISE
  - e. Weight loss of >5% in past three months for any reason other than post-partum weight loss. Participants taking weight loss drugs or using preparations taken for intended weight loss are excluded.
  - f. Likely to move away from participating clinics in next two years
  - g. Women of childbearing potential who are unwilling to use adequate contraception
  - h. Current (or anticipated) pregnancy and lactation.
  - i. Major psychiatric disorder that, in the opinion of clinic staff, would impede the conduct of RISE
10. Additional conditions may serve as criteria for exclusion at the discretion of the local site.

Further details pertaining to exclusion criteria are specified in the Manual of Procedures.

**CONFIDENTIAL**

### ***3.7 Randomization***

Randomization is stratified by clinical center and by prediabetes vs. diabetes status to ensure balance among the treatment groups with respect to anticipated differences in the participant populations. For each clinical center, the Coordinating Center (CoC) will generate two randomization schemes using a permuted block design. In this way, sample sizes across the four treatment arms will remain relatively equivalent as the trial progresses. The clinical center staff will use a computer-based system to input eligibility data and receive a random treatment assignment.

### ***3.8 Masking***

During the run-in period, participants will take metformin placebo and inject saline to assess compliance with possible study medications. After randomization, the metformin and placebo medications will be masked through a metformin-matched placebo. The insulin followed by metformin and liraglutide plus metformin arms will be unmasked.

Because the primary outcomes are based on a single set of measurements taken 3-months following medication withdrawal, the outcome measurements are inherently masked to both participants and investigators. Participants and clinical center staff will be masked to study results until after the final outcome measurements are complete.

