### **3.2 Primary Outcomes**

The primary objective of the RISE Study is to evaluate the effects of randomized treatment on  $\beta$ -cell function, measured by hyperglycemic clamp techniques. Given that insulin and C-peptide are both used in quantifying  $\beta$ -cell function, each of them will be measured in certain or all tests in part to avoid the problem of collinearity when performing the statistical analyses.

Two co-primary outcomes are specified:

- $\beta$ -cell function measured as the **second phase response (steady-state of the hyperglycemic clamp)** (100-120 minutes of glucose infusion) [64]. This will be calculated as mean C-peptide at steady state, adjusted for insulin sensitivity using the hyperglycemic clamp-derived measure of insulin sensitivity (glucose disposal rate/insulin: GDR/I).
- $\beta$ -cell function measured as **AIRmax (arginine-induced acute insulin response at hyperglycemic glucose;  $\beta$ -cell secretory capacity)** [30]. This will be calculated as the incremental area under the C-peptide curve from 0-10 minutes following arginine injection at a plasma glucose  $\geq 450$  mg/dl, adjusted for insulin sensitivity measured by the hyperglycemic clamp.

Overall, for primary and secondary outcomes we will use the insulin sensitivity measured during steady state of the hyperglycemic clamp (glucose disposal rate [derived from the steady state glucose infusion rate] divided by steady state plasma insulin concentration 100-120 min) for adjustment of  $\beta$ -cell function measures [69].

The main analysis will evaluate the effect of study treatments to induce durable improvement in these primary outcome measures of  $\beta$ -cell function, by comparing each treatment against placebo following a 3-month medication washout. The study will be analyzed under the intention-to-treat principle.

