**CONFIDENTIAL**

The clamp procedure will incorporate 3 main sets of blood sampling for the planned outcome measures: first phase (0-10 minutes); second phase (100-120 minutes); and maximal stimulated responses (from 10 minutes before arginine until 10 minutes after arginine). To guide the clamp, a small volume of arterialized venous blood will be obtained at 5-min intervals throughout for clamp for measurement of plasma glucose concentration and titration of the dextrose infusion.

For the OGTT and clamp measures, participants will be asked to refrain from vigorous exercise and tobacco use for 24 hours before the baseline measures. Study medications will be withheld the morning of testing.

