## **7.4 Risk Management**

Glucose management (including study medications) will be provided free of charge to RISE Study participants while participating in the study. Participants will receive training about the proper use of hypoglycemic medications as well as education about the symptoms, causes and response to episodes of hyper- and hypoglycemia. Participants who develop symptomatic hypo- or hyperglycemia, or experience any side effects of medications or study procedures will be instructed to call the clinical site. The following procedures will be implemented to minimize risk to participants:

- *Hyperglycemia:* Participants will be instructed regarding the signs and symptoms of hyperglycemia and are to call the clinic with any concerns. To minimize the risk of symptomatic hyperglycemia, the following procedures will be followed:
  - If HbA1c >7% at any routine quarterly visit, therapy will be invigorated by frequent telephone contact and/or visits to encourage optimal medication adherence and lifestyle choices. HbA1c will be obtained at the next quarterly visit. If HbA1c remains >7% but  $\leq$ 8%, frequent contact will be maintained.
  - If HbA1c >8.0% at any routine quarterly visit, therapy will be invigorated and HbA1c will be repeated after 6 weeks. If it remains >8.0%, outcome assessment will be scheduled in 2 weeks (i.e., regardless of time since randomization).
  - If at any time – either a routine visit or when a participant is brought in due to symptoms – the HbA1c >9%, the HbA1c will be repeated within 2 weeks and, if confirmed, the participant will be scheduled for immediate outcome measurement.

- Metabolic decompensation: In the unlikely event that a study subject develops metabolic decompensation, defined as hyperglycemia (plasma glucose >300 mg/dl) accompanied by significant symptoms (e.g., vomiting, dehydration, lethargy) and/or moderate or large urinary ketones, the participant will be evaluated to determine if temporary use of insulin therapy is required. Once insulin is started, the site will attempt to wean insulin within 4 weeks. If insulin cannot be weaned off within 4 weeks, the patient will be censored at that time.
- If outcome measurements are performed prior to the scheduled time points of 12 or 15 months, once completed the participant will be referred back to their primary care provider for further care.

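### Section 3.8 says timing alone masks the Month-15 outcomes, but timing does not hide assignment in the two open-label arms, so two of the three placebo comparisons lack the stated masking

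*Protocol*

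**What the plan says.** Protocol section 3.8 first sets out who is masked. Metformin and placebo are masked to each other by matched tablets. For the rest, "The insulin followed by metformin and liraglutide plus metformin arms will be unmasked". Section 3.4.2 agrees: "The two groups receiving injectables (i.e., liraglutide and insulin glargine) will not be masked to the intervention".

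The next paragraph of section 3.8 then turns to the outcomes. It begins "Because the primary outcomes are based on a single set of measurements taken 3-months following medication withdrawal" and concludes that "the outcome measurements are inherently masked to both participants and investigators". It adds, as a separate statement, that participants and site staff will not see study results until the last outcome measurements are done.

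On the measurement itself, section 6.1.3 has blood drawn every 5 minutes during the clamp for "measurement of plasma glucose concentration and titration of the dextrose infusion". Section 3.2 defines the insulin sensitivity used to adjust both co-primary outcomes as "glucose disposal rate [derived from the steady state glucose infusion rate] divided by steady state plasma insulin concentration 100-120 min". The SAP calls this quantity M/I and makes its logarithm one of the two variables in the joint 2-DF primary test.

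**The concern.** The two paragraphs of section 3.8 do not fit together. The first says that assignment is known in two of the four arms. The second says that the outcomes are masked to participants and investigators by virtue of when they are measured. Stopping a drug does not remove knowledge of which drug it was.

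This matters because the primary analysis does not rest on laboratory values alone. One component comes from an infusion rate that somebody adjusts during the test. If that person knows the arm, adjustments could differ by arm without intent. A protocol that declares the outcome masked removes the reason to put safeguards in place, and also the reason to report the limitation.

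**Working it through.** The protocol states no figure on this point, so there is none to reproduce. The check is a comparison of passages and a count.

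**1. Is assignment known?**

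| Arm | Masked? | Source |
|---|---|---|
| Metformin | Yes, matched placebo | Protocol 3.4.2, 3.8 |
| Placebo | Yes, matched placebo | Protocol 3.4.2, 3.8 |
| Insulin glargine, then metformin | No | Protocol 3.4.2, 3.8 |
| Liraglutide plus metformin | No | Protocol 3.4.2, 3.8 |

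Participants in the last two arms inject a drug they know. Site staff receive the assignment (section 3.7) and audit returned medication every three months (section 3.4.2). The investigator adjusts the insulin dose after hypoglycemia (section 7.3). Nothing in the 3-month washout undoes any of this.

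**2. Could the sentence mean only that results are hidden?** No. The following sentence makes that claim separately. The reason offered, the timing of the measurement, also has no bearing on who sees the results.

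**3. How many comparisons are affected?** Four arms give 4 × 3 / 2 = 6 pairs. Two masked arms give one pair masked on both sides, metformin versus placebo. So 6 − 1 = 5 pairs include an unmasked arm. Section 3.2 makes the comparison of each treatment with placebo the main analysis: 3 comparisons, of which 3 − 1 = 2 include an unmasked arm.

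**4. Does knowledge of the arm have a route to the outcome?** The steps are:
- the dextrose infusion is titrated during the clamp (section 6.1.3);
- its steady-state rate gives the glucose disposal rate (GDR), and GDR divided by insulin adjusts both co-primary measures (section 3.2);
- log M/I is the outcome of the first equation in the SAP's sample code, and its treatment coefficient is one of the two tested jointly.

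The Central Blood Laboratory runs the assays (section 11.1). That protects the insulin and C-peptide concentrations, but not the infusion rate in the numerator of M/I.

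**5. Does baseline adjustment help?** The baseline clamp precedes randomization (sections 3.4.1 and 4.4), so arm knowledge cannot have affected it. An arm-related effect that arises only at follow-up is not removed by adjusting for a baseline value that is free of it.

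**6. Is another safeguard stated?** Section 6.1 requires centrally trained and certified staff, which standardizes the procedure but does not mask anyone. Where the protocol wants blinded review it says so, as for the Safety Monitoring Committee in sections 7.2.2 and 8.4. Neither document says this of the clamp operator or the laboratory.

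**7. The sentence on study results.** Section 7.4 has sites respond to HbA1c: "If HbA1c >7% at any routine quarterly visit, therapy will be invigorated". HbA1c is a listed secondary outcome (section 3.3.1). Read literally, staff cannot be masked to all study results and also act on this one. The likely meaning is clamp and OGTT results, but the text does not say so.

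**The case against.** The strongest reply is that the design is openly described and already well controlled. The protocol calls the trial partially blinded and names the unmasked arms. Metformin versus placebo is double-blind. Peptide assays are central and site staff are kept from results. Both glucose goals are fixed, at 200 and above 450 mg/dl, and titration aims at the same goals in every arm from measured glucose. Steady state is the fixed 100-120 minute window. Training follows a Manual of Procedures with annual re-certification (section 11.3). That manual was not available here and may already deal with worksheets, labels, operator roles and rate adjustment.

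Most of this stands, and it narrows the point. It leaves operators less room than an uncontrolled procedure would, and it means that missing text in these two documents does not prove that the trial lacks the steps. It does not rescue the sentence in section 3.8, which gives timing as its only ground and makes no exception for the open arms. If the manual contains safeguards, section 3.8 should refer to them.

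It is also fair to say that quarterly HbA1c monitoring is described openly, so the wording on study results needs a clarification and no more.

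**Conclusion.** The masking claim in section 3.8 is wrong as written for the insulin glargine and liraglutide arms. It holds for metformin versus placebo, through the matched tablets and not through the timing. Two of three placebo comparisons, and five of six pairwise comparisons, lack the stated masking. M/I, part of the primary analysis, depends on an infusion rate titrated by an operator whom neither document masks to arm.

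This rests on the two documents alone, without the Manual of Procedures. A reader might infer four stronger things that they do not support:

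- **That bias occurred, or that the false-positive rate rises by a given amount.** The documents give no size for an operator effect. Any error rate would rest on an invented shift, and a simple two-arm calculation would also ignore the closed testing in section 9.1.
- **That operators decide when steady state is reached.** The protocol fixes the window at 100-120 minutes.
- **That site staff titrate the infusion by hand.** The protocol says that it is titrated and that trained, certified staff perform procedures. It does not describe the method or name the operator.
- **That the outcomes in these arms are wholly open-label.** Assays are central, and nothing says that the laboratory knows the arm.

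Leaving the injectable arms open is a defensible choice. The error is to state a protection that those arms do not have.

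**What to change.** In section 3.8, limit the masking claim to metformin versus placebo. State that participants and site staff know the assignment in the other two arms, and say whether clamp operators and the laboratory are masked to arm. Then:

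1. Leave the arm off clamp worksheets and sample labels at Months 12 and 15.
2. Apply one written infusion-adjustment rule to all arms, keeping the existing 100-120 minute window.
3. Have the Coordinating Center compute M/I and the C-peptide measures with the arm code removed.
4. Where existing staffing allows, use clamp operators who do not dispense or titrate for that participant. The documents do not describe site staffing, so this should not be mandatory.
5. Clarify that study results, in the masking sentence, means clamp and OGTT outcome results, so that it agrees with section 7.4.

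The cost is minor worksheet and scheduling work and a less favourable masking statement. If the clamps are already complete, the wording correction, the computation without the arm code and disclosure of the limitation can still be done.
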